### **42) Adverse Events and Classifications**

AE and AE subcategories are defined per GCP and CFR.

### **43) Adverse Event (AE)**

An AE is any untoward medical occurrence in a subject, which does not necessarily have a causal relationship with the treatment. An AE can be any unfavorable and unintended sign (such as an abnormal laboratory finding), symptom, or disease temporarily associated with the use of the study device, whether it is considered to be study device related. This includes any newly occurring event or previous condition that has increased in severity or frequency since enrollment in the study.

### **44) Serious Adverse Event (SAE)**

An adverse event will be considered serious if it meets at least one of the following criteria, regardless of causality or relationship to the study device:

Document Title: Colonoscopy: Demonstrating Effective Salvage of Inadequate Colonoscopies Utilizing the Pure-Vu EVS System	Outpatient	Document No. CL00052	Amendment 2.0	Page 32 of 46
---	------------	--------------------------------	-------------------------	---------------

- Death- results in fatality
- Life-threatening – subject was at an immediate risk of death from the reaction as it occurred.
  - Life threatening means that the subject was, in the view of the investigator, at immediate risk of death from the reaction as it occurred. This does not include an AE that, if more severe, might have caused death.
- Hospitalization (Initial or Prolonged) - Requires inpatient hospitalization or prolongs a hospital stay during the period of the therapy and/or within 24 hours after completion of study exit.
- Disability or Permanent damage - A substantial disruption of a person's ability to conduct normal life's functions.
- Congenital anomaly/birth defect - If exposure to the device prior to conception or during pregnancy may have resulted in an adverse outcome in a child.
- Requires intervention to prevent permanent damage - an intervention is required to prevent permanent damage.
- Important Medical Event - Events that may not result in death, be life-threatening, or require hospitalization may still be considered SAEs when, based upon appropriate medical judgment, they are felt to jeopardize the subject and may require medical or surgical intervention to prevent one of the outcomes listed above.

## 45) Adverse Device Effect (ADE)

An Adverse Device Effect (ADE) is an AE related to the use of an investigational medical device. This definition includes AEs resulting from insufficient or inadequate instructions for use, deployment, implantation, installation, or operation, or any malfunction of the investigational medical device.

This definition includes any event resulting from use error or from intentional misuse of the investigational medical device.

## 46) Serious Adverse Device Effect (SADE)

A Serious Adverse Device Effect is an anticipated adverse device effect that has resulted in any of the consequences characteristic of an SAE.

Document Title: Colonoscopy: Demonstrating Effective Salvage of Inadequate Colonoscopies Utilizing the Pure-Vu EVS System	Outpatient	Document No. CL00052	Amendment 2.0	Page 33 of 46
---	------------	--------------------------------	-------------------------	---------------

#### **47) Unanticipated Adverse Device Effect (UADE)**

An Unanticipated Adverse Device Effect is an adverse device effect which by its nature, incidence, severity, or outcome has not been identified in the current version of the risk analysis report.

#### **48) Unanticipated Serious Adverse Device Effect (USADE)**

An Unanticipated Serious Adverse Device Effect is a serious adverse device effect which by its nature, incidence, severity, or outcome has not been identified in the current version of the risk analysis report.

#### **49) Classification of Event Severity, Relationship and Outcomes**

#### **50) Adverse Event Severity Classification**

Severity will be defined according to the following criteria:

- Mild: Awareness of event, but easily tolerated
- Moderate: Discomfort enough to cause some interference with activities of daily living (ADL)
- Severe: Considerable interference with ADL, may be incapacitating and may require hospitalization

An AE can be classified as severe and not deemed a SAE. Similarly, a SAE is not automatically severe in nature.

#### **51) Adverse Event Relationship Classification**

Relationship to study device administration will be determined as follows:

- *No Relationship*: No relationship between the AE and the administration of study device and a known relationship to other etiologies such as concomitant medications, procedure, or subject's clinical state.
- *Possible Relationship*: An AE that follows a reasonable temporal sequence from administration of the study device and follows a known response pattern to the study device but could have been produced by the participant's clinical state or by other therapies.
- *Probable Relationship*: An AE that follows a reasonable temporal sequence from administration of the study device; follows a known response pattern to the study

Document Title: Colonoscopy: Demonstrating Effective Salvage of Inadequate Colonoscopies Utilizing the Pure-Vu EVS System	Outpatient	Document No. CL00052	Amendment 2.0	Page 34 of 46
---	------------	--------------------------------	-------------------------	---------------

device; and cannot be reasonably explained by the known characteristics of the participant's clinical state or by other therapies.

- *Definite Relationship*: An AE that follows a plausible temporal sequence from administration of the study device and follows a known response pattern to the study device. The reaction cannot be reasonably explained by the known characteristics of the subject's clinical state or other therapies administered to the subject.
- *Unknown/Impossible to Determine*: Given the information available, sequence and timing of events, it is unknown or impossible to determine the relationship of the AE with the study device.

## 52) Adverse Event Outcome Classification

Outcome of the event will be defined according to the following:

- *Resolved*: The event has fully resolved at the end of the study.
- *Resolved with sequelae*: The event has resolved but retained pathological conditions resulting from the prior disease or injury.
- *Ongoing*: The event is ongoing at the end of the study.
- *Death*: This event is determined to be the cause of death.

## 53) Device Deficiencies

A device deficiency is an inadequacy of a medical device related to its identity, quality, durability, reliability, safety, or performance, such as malfunction, misuse or use error and inadequate labeling.

All device deficiencies will be documented, and the device should be returned to Motus GI for analysis, if possible. Instructions for returning the investigational device will be provided. Device deficiencies should also be documented in the subject's medical record.

Device deficiencies are NOT AEs. However, if there is an AE that results from a device deficiency, that specific event would be recorded on the appropriate CRF.

## 54) Adverse Event Recording and Reporting

Assessment of the occurrence of an AE will be based on changes in the subject's signs and symptoms. AEs will be monitored until a subject completes the study unless the Investigator

Document Title: Colonoscopy: Demonstrating Effective Salvage of Inadequate Colonoscopies Utilizing the Pure-Vu EVS System	Outpatient	Document No. CL00052	Amendment 2.0	Page 35 of 46
---	------------	--------------------------------	-------------------------	---------------

determines the event is related to the investigational device, in which case they will be monitored until resolution if possible. Medical care will be provided, as defined in the informed consent, for any AE related to study participation. AEs will be collected on an AE eCRF and applicable source documentation.

The following should not be considered an AE:

- A condition requiring a preplanned procedure unless the condition worsened since screening
- A preexisting condition found as a result of screening, unless the condition has worsened since enrollment.

All relevant AEs observed during this study, regardless of severity or relationship to the study device will be recorded on the appropriate eCRF. All relevant AEs are associated complications expected during colonoscopies, use of the Pure-Vu System, bowel preparation or anesthesia. It will be the responsibility of the reporting PI to determine if the AE is relevant.

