## **10) Risk to Benefit Ratio**

## **11) Anticipated Risks Associated with the Study Device**

The potential risks of having a colonoscopy may include death, colon perforation, infection, bleeding, swelling of the colon tissue, hemorrhoids and anal tearing, mucosal trauma, rectal/anal bleeding, abdominal pain, nausea, vomiting and bloating feeling; in rare instances, there might be changes in a subject's heartbeat, low blood pressure or lack of oxygen as a result from the anesthesia. The risks associated with the specific use of Pure-Vu are expected to be similar to colonoscopies. There may be other risks that are unknown and cannot be foreseen. As with any colonoscopy procedure there are risks associated missed lesions, bowel perforation, pain, or bleeding. The risks associated with the specific use of Pure-Vu are expected to be comparable to standard colonoscopies. Also, risks have been mitigated to the furthest extent as required by regulatory bodies. Based on low adverse event rates in past studies as well as risk mitigations per the applicable standards, the Pure-Vu System does not introduce significant additional risk to patients.

Document Title: Colonoscopy: Demonstrating Effective Salvage of Inadequate Colonoscopies Utilizing the Pure-Vu EVS System	Outpatient	Document No. CL00052	Amendment 2.0	Page 21 of 46
---	------------	--------------------------------	-------------------------	---------------

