## **55) Reporting Responsibilities**

An investigator shall submit to the sponsor and to the reviewing IRB a report of any SAEs, ADEs, SADEs, UADEs, USADEs, and device deficiencies that could have led to a serious adverse device effect occurring during an investigation within 24 hours of learning of the event, but in no event later than 10 working days after the investigator first learns of the effect. The sponsor will evaluate all AEs and device malfunctions and evaluate whether those are complaints and meet FDA's requirements for MDR reporting. These events will be reportable per the complaint procedure and FDA's MDR regulation (21 CFR Part 803).

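### Section 54 ties eCRF entry of adverse events to their being expected, so an unexpected, non-serious event not treated as a device effect can be left off, and the section 51 causality scale adds to the gap

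*Protocol*

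**What the plan says.** Section 54 of the protocol contains two statements on what goes on the eCRF.

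- The first carries no condition: "AEs will be collected on an AE eCRF and applicable source documentation".
- The second, later in the section, is restricted: "All relevant AEs observed during this study, regardless of severity or relationship to the study device will be recorded on the appropriate eCRF". The term is then explained: "All relevant AEs are associated complications expected during colonoscopies, use of the Pure-Vu System, bowel preparation or anesthesia". The decision rests with the site: "It will be the responsibility of the reporting PI to determine if the AE is relevant".

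Other sections bear on the same events:

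- Section 43 defines the AE broadly: "An AE is any untoward medical occurrence in a subject, which does not necessarily have a causal relationship with the treatment".
- Section 11 concedes, after listing known complications, that "There may be other risks that are unknown and cannot be foreseen".
- Section 53 says of device deficiencies that "if there is an AE that results from a device deficiency, that specific event would be recorded on the appropriate CRF".
- Section 55 sets a separate expedited route: "An investigator shall submit to the sponsor and to the reviewing IRB a report of any SAEs, ADEs, SADEs, UADEs, USADEs, and device deficiencies". The deficiencies meant are those that could have led to a serious device effect. The same section has the sponsor assess all AEs.
- Section 51 makes a recognised pattern of response to the device part of the definition of Possible, Probable and Definite. No Relationship requires a known link to some other cause.
- Section 41 and the secondary safety endpoint in the synopsis summarise the events attributed, definitely or potentially, to Pure-Vu.

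**The concern.** A recording rule decides what can ever be analysed, and no analysis plan can recover an event that was never entered. Here the restricted rule admits events of a kind already expected and is silent on the rest. For a device study that is the wrong way round: known complications are the easiest to recognise and attribute, while an effect of a new kind is the hardest.

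Two sites could handle the same unexpected, non-serious event differently, and each could point to a sentence in section 54. The site that leaves it out would still be following a stated rule. A monitor comparing the eCRF with source records under section 64 could see the omission but would face the same two sentences when deciding whether it is a deviation. An event missing from the eCRF is also harder for the sponsor to re-assess for attribution later.

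**Working it through.** No plan figure is involved and no under-count can be calculated. The check sets the passages side by side.

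**Step 1: the literal logic of section 54.** If every relevant AE is an expected complication, then an AE of an unexpected kind is not relevant. The second rule requires entry of relevant AEs only, so it does not require this one. The first rule, taken alone, does. The second rule waives severity and relationship to the device as filters. Two filters remain, both judged by the principal investigator: association with one of four exposures (colonoscopy, Pure-Vu, bowel preparation, anesthesia) and expectedness. The first is a reasonable screen against unrelated illness; the second causes the problem.

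**Step 2: which unexpected events have another route.** Split them by seriousness and by whether they are treated as an adverse device effect (ADE):

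| Unexpected AE | Treated as ADE | Not treated as ADE |
|---|---|---|
| Serious | Section 55 | Section 55, as SAE |
| Non-serious | Section 55, as ADE | No section 55 route |

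Three of the four cells reach the sponsor and IRB. The fourth depends on section 54, unless the event results from a device deficiency (section 53). Section 30 has new or worsening events at the follow-up call documented, but does not name the eCRF. Section 55 is likewise a reporting route and does not itself require eCRF entry.

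**Step 3: how a novel device effect is rated under section 51.** Take an event with plausible timing, no recognised device pattern and no other known cause:

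- No Relationship: fails, because it needs a known other cause.
- Possible, Probable, Definite: all three fail, because each needs a known response pattern.
- Unknown: fits.

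So 1 of 5 categories is open to it. Section 41 does not say whether Unknown counts as potentially attributed, so the event may fall outside the summary.

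**Step 4: what stays recordable.** The first sentence of section 11 alone names 16 complication types: death, perforation, infection, bleeding, colon swelling, hemorrhoids, anal tearing, mucosal trauma, rectal/anal bleeding, abdominal pain, nausea, vomiting, bloating, heartbeat change, low blood pressure and lack of oxygen. All are expected kinds and pass the section 54 filter.

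**The case against.** The best defence is that section 54 moves from the general to the specific. The first sentence says where AEs are recorded and does not say that all are. The later paragraph sets the scope, and *expected* may have been meant loosely, as *associated with*. Limiting collection to relevant events is a recognisable choice in a pragmatic, post-market study of a cleared device. That removes some of the force of calling it a contradiction. It does not rescue the wording: if the later paragraph governs, the expectedness condition governs too, and it still does not fit section 43 or the sponsor's review of all AEs in section 55.

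The defence is right on three further points.

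- Expectedness is not the only filter. Association with the four exposures is another and has a sensible purpose. Abolishing all relevance screening would burden a cohort of about 1,067 subjects. At the planned 12% inadequate-preparation rate, only about 0.12 × 1,067 ≈ 128 of them would be candidates for the device.
- The uncovered cell lies mostly outside the planned summary, which is confined to attributed events.
- A repair limited to SAEs and possibly related AEs would not work alone, because section 51 denies a novel effect the Possible rating.

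A reader might go further and infer that unexpected SAEs or device effects go unreported, or that the comparison of SAE rates with the published 2.8% is compromised. The protocol does not support this: section 55 requires those reports with no expectedness condition. Nor does it say that the section 51 rating decides whether an event is an ADE, so an Unknown rating cannot be taken to remove an event from that route. Section 46 limits serious adverse device effects to anticipated ones, which sits badly with the unanticipated class in section 48. A reader might see a reporting gap there, but section 55 gives both classes the same recipients and deadlines, so only the label is affected.

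**Conclusion.** The point holds in a limited form. Section 54 as written lets an AE of unexpected nature be left off the eCRF. After sections 53 and 55 are allowed for, the exposed group is mainly unexpected, non-serious events not treated as device effects. Section 51 compounds this, because a novel effect with no other known cause can only be rated Unknown and may be missed by the attributed-event summary.

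The effect on the stated safety analysis is modest. Its size cannot be derived, since the protocol gives no rate for such events. The conclusion rests on a literal reading of *expected* and on sites acting on the later paragraph of section 54. The loss in the summary also depends on how Unknown ratings are tabulated, which the SAP may settle. The wording should be corrected because the two conditions together screen out the kind of event that the safety summary most needs to catch.

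**What to change.** Reconcile sections 54, 43, 55 and 51 in one amendment.

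- **Section 54.** Delete expectedness as a condition for entry. Require eCRF entry of all SAEs, and of any AE associated in time or plausibly with colonoscopy, Pure-Vu, bowel preparation or anesthesia, whether or not it was expected. Record expectedness as a coded field. The investigator's judgement that an event is clearly unrelated to all four may stay.
- **Section 51.** Do not make a known response pattern a necessary condition for Possible.

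The two edits belong together. The first gets the event into the database; the second allows it to be attributed and summarised. Deleting the word *anticipated* in section 46 at the same time would be a label correction and would change no reporting route.

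The cost is wording changes, one added eCRF field and somewhat more AE data entry at sites.

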## **55) Reporting Responsibilities**

An investigator shall submit to the sponsor and to the reviewing IRB a report of any SAEs, ADEs, SADEs, UADEs, USADEs, and device deficiencies that could have led to a serious adverse device effect occurring during an investigation within 24 hours of learning of the event, but in no event later than 10 working days after the investigator first learns of the effect. The sponsor will evaluate all AEs and device malfunctions and evaluate whether those are complaints and meet FDA's requirements for MDR reporting. These events will be reportable per the complaint procedure and FDA's MDR regulation (21 CFR Part 803).

## **56) Ethics and Compliance**

## **57) Statement of Compliance**

This clinical investigation will be conducted in accordance with the ethical principles that have their origin in the Declaration of Helsinki, ICH-GCP, and any regional or national regulations, as appropriate.

Document Title: Colonoscopy: Demonstrating Effective Salvage of Inadequate Colonoscopies Utilizing the Pure-Vu EVS System	Outpatient	Document No. CL00052	Amendment 2.0	Page 36 of 46
---	------------	--------------------------------	-------------------------	---------------

This may include an inspection by Motus GI representatives and/or Regulatory Authority representatives at any time. The investigator must agree to the inspection of study-related records by the Regulatory Authority/ Motus GI representatives and must allow direct access to source documents to the Regulatory Authority/ Motus GI representatives. Regulatory Authority approvals/authorizations/notifications, where required, will also be in place and fully documented prior to study start.

## **58) Protocol Compliance**

No changes to the study protocol will be permitted without the written approval from Motus GI and the IRB. The investigator must notify Motus GI and the reviewing IRB of any deviation from the study protocol when specific to the protection of the life or physical well-being of a subject in an emergency. Such notice must be given as soon as possible. Except in such an emergency, prior written approval by Motus GI is required for changes in or deviations from the protocol. If these changes or deviations affect the scientific soundness of the Plan or the rights, safety, or welfare of human subjects the IRB will also be notified. All other deviations will be reported per the site's IRB deviation policy. Should any deviations from the study protocol occur, these will be reviewed by Motus GI for their clinical significance. If the event is performed without written approval from all parties, the investigator may be terminated from the study.

## **59) Institutional Review Board (IRB)**

Documented approval from the appropriate Institutional Review Board (IRB) per 21 CFR Part 56 will be obtained for all participating centers prior to study start, according to ICH GCP, local laws, regulations, and organization. When necessary, an extension, amendment, or renewal of the IRB approval must be obtained. The IRB must supply to the sponsor a list of the IRB membership and a statement to confirm that the IRB is organized and operates according to GCP and applicable laws and regulations.

## **60) Subject Informed Consent**

Prior to the beginning of the trial, the investigator must have the IRB written approval of the ICF and any other written information to be provided to subjects. The written approval of the IRB together with the approved ICFs must be filed in the study files.

The process of obtaining informed consent must be in accordance with applicable regulatory requirement(s) (e.g. 21 CFR Part 50) and must adhere to GCP and to the ethical principles

Document Title: Colonoscopy: Demonstrating Effective Salvage of Inadequate Colonoscopies Utilizing the Pure-Vu EVS System	Outpatient	Document No. CL00052	Amendment 2.0	Page 37 of 46
---	------------	--------------------------------	-------------------------	---------------

originating in the Declaration of Helsinki. Written/electronic informed consent must be obtained before any study specific procedure takes place. Participation in the trial and date of informed consent given by the subject should be documented appropriately in the subject files.

